#### 8.1.1 Adverse Events Definitions

### 8.1.1.1 Adverse Events (21 CFR 312.32(a))

An adverse event (AE) is defined as any untoward medical occurrence associated with the use of a drug in humans, whether or not considered drug related. An AE (also referred to as an adverse experience) can be any unfavorable and unintended sign (e.g., an abnormal laboratory finding), symptom, or disease temporally associated with the use of a drug and does not imply any judgment about causality. An adverse event can arise with any use of the drug (e.g., off-label use, use in combination with another drug) and with any route of administration, formulation, or dose, including an overdose.

### 8.1.1.2 Suspected Adverse Reaction (21 CFR 312.32(a))

Suspected adverse reaction means any adverse event for which there is a reasonable possibility that the drug caused the adverse event. For the purposes of IND safety reporting, 'reasonable possibility' means there is evidence to suggest a causal relationship between the drug and the adverse event. A suspected adverse reaction implies a lesser degree of certainty about causality than adverse reaction, which means any adverse event caused by a drug.

### 8.1.1.3 Unexpected (21 CFR 312.32(a))

An adverse event or suspected adverse reaction is considered "unexpected" if it is not listed in the investigator brochure or is not listed at the specificity or severity that has been observed; or, if an investigator brochure is not required or available, is not consistent with the risk information described in the general investigational plan or elsewhere in the current application, as amended. For example, under this definition, hepatic necrosis would be unexpected (by virtue of greater severity) if the investigator brochure referred only to elevated hepatic enzymes or hepatitis. Similarly, cerebral thromboembolism and cerebral vasculitis would be unexpected (by virtue of greater specificity) if the investigator brochure listed only cerebral vascular accidents. "Unexpected," as used in this definition, also refers to adverse events or suspected adverse reactions that are mentioned in the investigator brochure as occurring with a class of drugs or as anticipated from the pharmacological properties of the drug but are not specifically mentioned as occurring with the particular drug under investigation.

Clinical Study Protocol TTHX-002

Confidential and Proprietary

Amendment 7.0: September 22, 2022

### 8.1.1.4 Serious Adverse Event (21 CFR 312.32(a))

An adverse event or suspected adverse reaction is considered "serious" if, in the view of either the investigator or sponsor, it results in any of the following outcomes:

- Death,
- a life-threatening adverse event,
- inpatient hospitalization or prolongation of existing hospitalization,
- a persistent or significant incapacity or substantial disruption of the ability to conduct normal life functions, or
- a congenital anomaly/ birth defect

Important medical events that may not result in death, be life-threatening, or require hospitalization may be considered serious when, based upon appropriate medical judgment, they may jeopardize the patient or subject and may require medical or surgical intervention to prevent one of the outcomes listed in this definition. Examples of such medical events include allergic bronchospasm requiring intensive treatment in an emergency room or at home, blood dyscrasias or convulsions that do not result in inpatient hospitalization, or the development of drug dependency or drug abuse.

# 8.2 Adverse Events Reporting

#### **8.2.1** Adverse Event Term

Adverse events must be reported using standard medical terminology. The use of abbreviations (standard and nonstandard) should be avoided to help ensure a clear understanding of the event. An example of a standard abbreviation that may have several meanings is "MI" which could mean "myocardial infarction" or "mitral insufficiency." All AE terms will be coded using a standardized dictionary (i.e., Medical Dictionary for Regulatory Activities [MedDRA]).

- Generally, when reporting a well-known and understood condition, it is preferable to report the overall diagnosis rather that the individual signs and symptoms; the exception to this rule in this study is when the subject experiences an injection site reaction.
- The term "intermittent" should be avoided as the duration and incidence of events helps in understanding the safety profile of the study drug.

#### **8.2.2** Adverse Event Severity

Adverse events will be reported at the highest experienced. Adverse events severity will be graded according to the criteria described in Table 11.

Trefoil Therapeutics, Inc.

Clinical Study Protocol TTHX-002

Confidential and Proprietary

Amendment 7.0: September 22, 2022

**Table 11: Severity Grading Guideline for Adverse Events** 

Grade	Description
Mild	Asymptomatic or mild symptoms;
	Clinical or diagnostic observations only;
	Intervention not indicated
Moderate	Minimal, local or noninvasive intervention indicated;
	Limiting age-appropriate instrumental ADL*
Severe	Medically significant;
	Hospitalization or prolongation of hospitalization indicated;
	Disabling;
	Limiting self-care ADL**

Adapted from NCI-CTCAE V5.0

Note: A Semi-colon indicates 'or' within the description of the grade.

#### **8.2.3** Adverse Event Duration

The start date (the date that the event was first noticed) and the end date (the date that the event had completely resolved or returned to baseline) will be recorded. If the exact date is not known, the best estimate should be reported.

### **8.2.4** Adverse Event Causality

Where the Investigator assessment of the relationship of the AE to investigational product rests on medical judgment, the determination must be made with the appropriate involvement of the Investigator, or, if the Investigator is not a physician, a designated sub-Investigator who is a physician. Assessment of causality should be performed in accordance with the definition of SAR in Section 8.1.1.2.

Using the following criteria, Investigators will assess whether there is a reasonable possibility that the study treatment (drug or procedure) caused or contributed to the AE.

### Related

There is a "reasonable possibility" to suggest a causal relationship between the study treatment and the adverse event based on evidence.

- The Investigator should use the following criteria when assessing causality:
- Is the AE a known side effect/ adverse reaction to the study treatment or other therapies in this treatment class?
- Is there a reasonable temporal relationship between the start of the AE and study treatment administration?
- Did the AE improve when the study treatment was stopped?
- Did the AE recur when the study treatment was resumed, if applicable?
- Can the AE be easily attributed to a comorbid condition or concomitant medication/ treatment?

\*Instrumental ADL refer to preparing meals, shopping for groceries or clothes, using the telephone, managing money, etc.

\*\*Self-care ADL refer to bathing, dressing and undressing, feeding self, using the toilet, taking medications, and not bedridden.

Clinical Study Protocol TTHX-002

Confidential and Proprietary

Amendment 7.0: September 22, 2022

### **Not Related**

There is NOT a "reasonable possibility" to suggest a causal relationship between the study treatment and the adverse event based on evidence.

#### 8.2.5 Adverse Event Seriousness

Please report SAE criteria using the following guidelines:

#### Death

Report if you suspect that the death was an outcome of the adverse event and include the date if known.

### Life-threatening

Report if suspected that the patient was at substantial risk of dying at the time of the adverse event or use or continued use of the device or other medical product might have resulted in the death of the patient.

### **Hospitalization (initial or prolonged)**

Report if admission to the hospital or prolongation of hospitalization was a result of the adverse event. Emergency room visits that do not result in admission to the hospital should be evaluated for one of the other serious outcomes (e.g., life-threatening; required intervention to prevent permanent impairment or damage; other serious medically important event).

### **Disability or Permanent Damage**

Report if the adverse event resulted in a substantial disruption of a person's ability to conduct normal life functions, i.e., the adverse event resulted in a significant, persistent or permanent change, impairment, damage or disruption in the patient's body function/structure, physical activities and/or quality of life.

### **Congenital Anomaly/Birth Defect**

Report if you suspect that exposure to a medical product prior to conception or during pregnancy may have resulted in an adverse outcome in the child.

### **Other Serious (Important Medical Events)**

Report when the event does not fit the other outcomes, but the event may jeopardize the patient and may require medical or surgical intervention (treatment) to prevent one of the other outcomes. Examples include allergic brochospasm (a serious problem with breathing) requiring treatment in an emergency room, serious blood dyscrasias (blood disorders) or seizures/convulsions that do not result in hospitalization. The development of drug dependence or drug abuse would also be examples of important medical events.

(https://www.fda.gov/safety/reporting-serious-problems-fda/what-serious-adverse-event)

#### **8.3 Serious Adverse Events Reporting**

Adverse events that meet the definition of serious require accelerated reporting. Investigators must report all Serious Adverse Events (SAEs) regardless of causality immediately (within 24 hours of learning of the event). SAEs will be reported by submitting a Serious Adverse Events Report (SAER) to:

Amendment 7.0: September 22, 2022

If adverse events of special interest (AESI) are identified during the study, Trefoil will notify Investigators and provide instructions for reporting. Deaths occurring within 1 year of study treatment and AESIs will be reported to Trefoil in the same time frame as SAEs.

Trefoil will be responsible for expedited safety reporting to regulatory authorities and principal investigators where clinical trials involving investigational product are being conducted.

### 8.4 Adverse Events of Special Interest

#### 9. STATISTICS

### 9.1 Sample Size

The sample size for this study was determined by clinical and practical rather than statistical considerations. Sixteen subjects in the active treatment group compared to 8 subjects in the non-treatment control group were planned during the study to provide a preliminary estimate of safety and efficacy.

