#### 4. TRIAL DESIGN

This is an open-label, multi-center study in which up to approximately 50 subjects with FECD who are scheduled for DWEK/DSO will be enrolled. Study subjects will be assigned to Study Treatment Group based on the Group(s) open at the time of treatment of the primary (first) eye; if a subject elects to have an eligible second (contralateral) eye treated, that "fellow" eye will be treated based on the Group(s) open at the time. The number of subjects per group in the study and per study treatment is summarized below in Table 7.

Amendment 7.0: September 22, 2022

Note: the study was amended to allow treatment of the contralateral eye. To avoid ambiguity the eye that was treated first will be referred to as the Study Eye (SE); the contralateral eye will be referred to as the Fellow Eye (FE).

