**Table 7: Study Groups and Number of Subjects** 

	TTHX1114	4 Regimen		
	Day	Dose	Number of Subjects	
Group 1	N/A	N/A	8 (Closed after 1 enrolled)	
	Day -3	10ng		
	Day 0	50ng	9.16	
Group 2	Day 7	10ng	8-16 (Closed after 9 enrolled)	
•	Day 14	10ng		
	Day 21	10ng		
Group 3	Day 0	100ng	20	
Group 4	Day 0	100ng	20	
	Day 7	30 or 50ng		
	Day 14	30 or 50ng		
	Day 21	30 or 50ng		
Group 1a	Weekly x 5	30 or 50ng	NA	
Group 3a	Weekly x4	30 or 50ng	NA	
·		 	up to 50	

[figure not shown]
Subject will be consented and screened for eligibility during the screening period prior to the scheduled DWEK/DSO procedure.

The study schema is presented in Figure 1 and Figure 2.

Confidential and Proprietary

Amendment 7.0: September 22, 2022

Figure 1: Study Treatment Schema

\*Subjects who have not sufficiently recovered by Day 28, may receive an additional dose of TTHX1114 following discussion with the Medical Monitor

Eligible subjects who do not wish to receive investigational product or who do not have a qualifying Fellow Eye will be assigned to Treatment Group 1.

Following preliminary safety and tolerability assessment of the 50ng IC injection in Group 2, Trefoil may elect to open Group 3 and Group 4

[figure not shown]
- Group 3 in which eligible subjects will be given a "1 and done" dosing regimen in which TTHX1114 will be administered as a 100ng/100mcL volume injection at the time of DWEK/DSO
- Group 4 in which eligible subjects will be given a 100ng/100mcL volume injection at the time of DWEK/DSO and then weekly injections of 30 or 50ng (30 or 50mcL) x3. Subjects in Group 4, who have not sufficiently recovered by Day 28, may receive an additional dose of TTHX1114 following discussion with the Medical Monitor

Following preliminary safety and efficacy evaluation in subjects who received TTHX1114, Trefoil may open enrollment in Groups 1a and 3a in which TTHX1114-naive subjects in Group 1 and subjects in Group 3 may be allowed to "roll-over" to a TTHX1114 regimen of up to 5 weekly injections of TTHX1114. To be eligible for Group 1a or Group 3a, subjects must continue to be eligible for the study (e.g., have a suitable fellow eye and not have had any severe suspected adverse reactions.

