#### 9.2 Analyses

The study includes a concurrent non-treatment control group. The active treatment group will be compared to the control group. In addition, descriptive statistics will be used to tabulate and summarize other efficacy variables and safety outcomes. Baseline and demographic characteristics will be presented. Continuous variables will be summarized by descriptive statistics (sample size, mean/ standard deviation, median, minimum and maximum). Discrete variables will be summarized by frequencies and percentages. Ocular AEs involving the study eye will be summarized by presenting the number and percentage of subjects having any ocular AE. Any other information collected (such as severity or relationship to study drug and intracameral injection) will be listed as appropriate.

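### Section 9.1 still gives the original 16 v 8 plan as the sample size, while Section 4 and Table 7 describe 1 control and 49 TTHX1114 subjects in three regimens (9, 20, 20)

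*Combined protocol and SAP*

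**What the plan says.** Section 9.1 (Sample Size) is the only sizing text in the statistics section. It opens with the basis: "The sample size for this study was determined by clinical and practical rather than statistical considerations". It then gives the numbers: "Sixteen subjects in the active treatment group compared to 8 subjects in the non-treatment control group were planned during the study", intended for a preliminary estimate of safety and efficacy. It gives no alpha, power, effect size, rate or dropout allowance.

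Section 4 (Trial Design) says "up to approximately 50 subjects with FECD who are scheduled for DWEK/DSO will be enrolled" and refers to Table 7 for the number per group. Table 7 lists:
- Group 1, the untreated control: "8 (Closed after 1 enrolled"
- Group 2: "8-16 (Closed after 9 enrolled"
- Group 3: "Group 3 Day 0 100ng 20"
- Group 4: "Group 4 Day 0 100ng 20", followed by weekly injections
- Groups 1a and 3a: no number, because they take subjects who roll over from Groups 1 and 3
- Total: up to 50

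Section 9.2 (Analyses) then says "The active treatment group will be compared to the control group".

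**The concern.** A reader who goes to the statistics section to learn how large the trial is, and how much it can show, finds one active group of 16 and a control of 8. Neither number describes the design in Section 4. No TTHX1114 group has 16 subjects, and the control has 1. There are three regimens, not one: Section 4.4 gives five injections in Group 2, one in Group 3 and four to five in Group 4.

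Two things are at stake. First, Section 9.1 ties its numbers to a preliminary estimate of safety and efficacy, so their relevance to that estimate depends on their being this trial's numbers. Second, Section 9.2 carries the single active group into the planned comparison. It is then unclear whether that group means Group 2 alone, another single regimen, or all 49 TTHX1114 subjects pooled. The active count, the total and the one-group description need correcting whatever is decided about the closed control.

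**Working it through.** **Can the stated size be reproduced?** No formula applies. Section 9.1 disclaims statistical sizing and supplies no inputs, so the check is a comparison of counts.

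**Section 9.1.** 16 + 8 = 24. The sum is mine; the protocol does not print 24.

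**Table 7, using the counts at closure.** 1 + 9 + 20 + 20 = 50, which matches the table's total exactly. On TTHX1114: 9 + 20 + 20 = 49. The fiftieth subject is the single Group 1 control.

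**Table 7, using the original targets.** 8 + 8 + 20 + 20 = 56 at the low end and 8 + 16 + 20 + 20 = 64 at the high end. Neither gives 50, so the total in Section 4 and Table 7 already reflects the closures. Section 9.1 does not.

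| | Section 9.1 | Section 4 and Table 7 |
|---|---|---|
| Active | 16, one group | 49, in groups of 9, 20 and 20 |
| Control | 8 | 1 (closed) |
| Sum | 24 | 50 |

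**Where 16 and 8 come from.** They equal the upper end of Group 2's planned range and Group 1's planned number in Table 7. Section 9.1 therefore describes Groups 1 and 2 as first planned. Groups 3 and 4 supply 20 + 20 = 40 of 50 subjects (80%) and do not appear in it.

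**What the group sizes give, as illustration only.** The documents give no success rate and no expected evaluable number, so both are assumptions here. The 95% half-width for one proportion is 1.96 × √(p(1−p)/n), by normal approximation. The smallest true adverse event rate with a 95% chance of at least one event is 1 − 0.05^(1/n).

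| n evaluable (independent) | half-width, p = 50% | half-width, p = 70% | half-width, p = 80% | smallest AE rate |
|---|---|---|---|---|
| 20 | ±22 points | ±20 | ±18 | 14% |
| 15 (assumes 5 of 20 not evaluable) | ±25 | ±23 | ±20 | 18% |
| 9 | ±33 | ±30 | ±26 | 28% |

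For example, 1.96 × √(0.25/20) = 0.219 and 1 − 0.05^(1/20) = 0.139. At n = 9 the normal approximation is rough; the exact 95% interval for 4 of 9 is 14% to 79%.

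**The case against.** The strongest defence is that Section 9.1 is written in the past tense and can be read as history. Table 7 supports that reading, since 8 and 16 were indeed planning figures for Groups 1 and 2. This softens the inconsistency but does not remove it: the sentence is not marked as superseded, and no current figure or cross-reference follows.

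Three further defences stand, and they limit the point:
- **The current sizes are in the protocol.** Section 4 and Table 7 state them plainly. A reader might infer from Section 9.1 that the trial's true size appears nowhere. That is not so; it is missing from the statistics section only.
- **No calculation fails.** A reader might infer a sample size or power error. The documents do not support that: the sizes are declared practical, and the Table 7 total adds up.
- **Group 3 against Group 4 is not a planned contrast.** With one control, a reader might take it to be the trial's main comparison and fault the plan for not giving its precision. Sections 9.2 and 9.3.1 plan only comparisons with control, and assignment follows whichever group is open, without randomisation.

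Section 9.3 promises a full statistical analysis plan before database lock. That may settle the analysis, but it does not correct the protocol's own sample size section.

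**Conclusion.** The inconsistency is real and modest in consequence. Section 9.1 gives 16 v 8; the design in the same amendment gives 49 on TTHX1114 in three regimens plus 1 control, up to about 50. The 16 v 8 size is not what this design delivers, and 40 of the 50 subjects fall outside the section that is meant to explain the sample size. The counts come directly from the protocol and rest on no assumption.

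The precision figures do rest on assumptions. They take a success rate the documents do not give, and they treat each group's count as independent evaluable subjects. The second may be optimistic. Section 9.3.1 assesses efficacy in the Per Protocol set, which requires complete treatment, a descemetorhexis of 4 to 5 mm and sufficient data. Section 6.1.2 lets a subject's fellow eye be re-enrolled in Group 3 or 4, so two eyes of one person may both contribute. The ±22 points for a group of 20 at a 50% rate is therefore an illustration, not a property of the trial.

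**What to change.** - Restate Section 9.1 with the Table 7 allocation (Group 1 = 1, closed; Group 2 = 9, closed; Group 3 = 20; Group 4 = 20; up to about 50), or cross-reference Table 7.
- Mark 16 v 8 as the superseded original plan.
- Keep the sentence saying that the sizes are practical rather than statistical.
- In Sections 9.1 and 9.2, replace the single active group with the three regimens, and say whether each is summarised separately or pooled.
- If precision is added, label it as illustrative, show a range of assumed rates and evaluable numbers as in the table above, and do not present Group 3 against Group 4 as a planned contrast.

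The cost is wording only: no extra subjects, visits or procedures. The downside is that the stated precision per regimen will look modest.

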#### 9.2 Analyses

The study includes a concurrent non-treatment control group. The active treatment group will be compared to the control group. In addition, descriptive statistics will be used to tabulate and summarize other efficacy variables and safety outcomes. Baseline and demographic characteristics will be presented. Continuous variables will be summarized by descriptive statistics (sample size, mean/ standard deviation, median, minimum and maximum). Discrete variables will be summarized by frequencies and percentages. Ocular AEs involving the study eye will be summarized by presenting the number and percentage of subjects having any ocular AE. Any other information collected (such as severity or relationship to study drug and intracameral injection) will be listed as appropriate.

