#### 9.3.1 Analysis Populations and Sets

The analysis sets for this clinical study are defined in accordance with *ICH E9 Guidance for Industry Statistical Principles for Clinical Trials*. The Full Analysis Set is intended to be the population which is as complete as possible and as close as possible to the intention-to-treat ideal. This is an open label study and not randomized, therefore the Full Analysis Set will include only subjects who have received any study treatment and will be the same as the Safety Population. Analysis sets are described below in Table 12.

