**Table 12: Analysis Sets** 

Analysis Set	Description of Population	Reference
Full Analysis Set*	
 
Received any study treatment (at least 1 complete or partial dose)
 
	ICH E9 (5.2.1)
Per Protocol Set	Met all eligibility criteria	ICH E9 (5.2.2)
	Have received all study treatments per protocol	
	
 
Underwent DWEK/DSO of 4 to 5mm
 
	
	
 
Have sufficient data collected for the accurate assessment of study endpoints
 
	

\*The Full Analysis Set will be used for the Safety Population

The Per Protocol Population will be used to assess the primary and secondary efficacy endpoints compared to the control group.

The Safety Population set includes all participants in participants who received any TTHX1114 and will be the population for safety outcomes; this population will be compared with the control group. Ocular AEs involving the study eye will be tabulated. Ocular AEs for the fellow eye and non-ocular AEs will be provided as a listing.

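### Section 9 still compares TTHX1114 with a concurrent untreated control, but Table 7 shows that control closed after one subject, so the comparison cannot support inference.

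*Combined protocol and SAP*

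**What the plan says.** Section 9.2 states in the present tense that "The study includes a concurrent non-treatment control group" and then that "The active treatment group will be compared to the control group". After Table 12, Section 9.3.1 makes the same commitment twice. For efficacy: "The Per Protocol Population will be used to assess the primary and secondary efficacy endpoints compared to the control group". For the Safety Population: "this population will be compared with the control group". The synopsis and the Group 1 description in Section 4 also still present Group 1 as a concurrent control arm.

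Table 7 in Section 4 gives the number of Group 1 subjects as "8 (Closed after 1 enrolled". Group 2 closed after 9, and Groups 3 and 4 are listed at 20 each. Assignment was not randomised: Section 4 sends to Group 1 the eligible subjects who "do not wish to receive investigational product or who do not have a qualifying Fellow Eye".

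Section 9.1 gives only the earlier sizes: "Sixteen subjects in the active treatment group compared to 8 subjects in the non-treatment control group were planned during the study". Section 9.3.1 adds that "the Full Analysis Set will include only subjects who have received any study treatment", and that this set is also the Safety Population. Section 9.3 leaves the detailed analysis to an SAP to be written before database lock.

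**The concern.** The design table was updated when Group 1 closed, but the statistics section was not. The only contrast that the visible text commits to, for primary and secondary efficacy and for safety, is against a group of one.

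Three things follow.

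- **No control variability.** One subject gives no SD. The treated-minus-control difference depends largely on how that subject did.
- **No exchangeability.** The rule for entering Group 1 was declining the drug or lacking a qualifying fellow eye, so even a larger Group 1 would have differed systematically from the treated groups. Groups 3 and 4 could open only after a safety look in Group 2, and no closing date is given for Group 1, so it cannot be confirmed that the control is concurrent with them.
- **Unclear analysis-set membership.** An untreated subject is outside the Full Analysis Set and Safety Population. Nothing in the Per Protocol criteria says how a subject due no TTHX1114 is handled.

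Someone who reads Section 9 or the synopsis will expect an estimate of what TTHX1114 adds to DWEK/DSO alone. The trial can no longer supply one.

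**Working it through.** **Inputs from the protocol.** Control n = 1 (planned 8); Group 2 n = 9 (planned 8 to 16); Groups 3 and 4 n = 20 each; total up to 50 (Table 7). Planned comparison 16 v 8 (Section 9.1). Day 28 endpoints: BCVA of 20/40 or better, and central corneal thickness (Section 4.1).

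**Assumptions.** The visible text gives no alpha, test, response rate or SD. Assumed here: two-sided alpha 0.05; Fisher's exact test for the binary endpoint; a t interval for the continuous one; true success rates of 30% v 70%, 20% v 80% and 10% v 90%, control first.

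**Step 1: the plan's own figures.** The 16 v 8 cannot be reproduced, because Section 9.1 says that statistical considerations did not set it. The Table 7 total can: 1 + 9 + 20 + 20 = 50. The planned sizes would give 8 + 8 + 20 + 20 = 56 to 8 + 16 + 20 + 20 = 64. The stated total of 50 is therefore matched by the closed group sizes, with one control. Pooling all treated subjects gives 9 + 20 + 20 = 49.

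**Step 2: smallest attainable p-value.** If the control fails and all m treated subjects succeed, the two-sided Fisher p is 1/(m + 1). With f treated failures (f small) it is (f + 1)/(m + 1).

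| Comparison | All treated succeed | One failure | Two failures |
|---|---|---|---|
| 1 v 9 | 1/10 = 0.100 | – | – |
| 1 v 20 | 1/21 = 0.048 | 2/21 = 0.095 | – |
| 1 v 49 | 1/50 = 0.020 | 2/50 = 0.040 | 3/50 = 0.060 |

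Significance is impossible against Group 2. Against a group of 20 it needs 20/20 successes and a failing control. Against all 49 it allows at most one treated failure.

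**Step 3: exact power.** Sum the binomial probabilities of every table with Fisher p ≤ 0.05. At 1 v 20 this is essentially (1 − p0) × p1^20; for 20% v 80%, 0.8 × 0.8^20 = 0.0092.

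| Comparison | 30% v 70% | 20% v 80% | 10% v 90% |
|---|---|---|---|
| 8 v 16 (planned) | 38% | 79% | 99% |
| 1 v 9 | 0 | 0 | 0 |
| 1 v 20 | 0.06% | 0.9% | 11% |
| 1 v 49 | <0.01% | 0.02% | 3.3% |

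**Step 4: precision for a mean.** One control has no SD, so the SD must be borrowed from the treated subjects. The 95% half-width in SD units is t(0.975, n1 + n2 − 2) × √(1/n1 + 1/n2).

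- 8 v 16: 2.074 × √(1/8 + 1/16) = 0.90
- 1 v 9: 2.306 × √(1 + 1/9) = 2.43
- 1 v 20: 2.093 × √(1 + 1/20) = 2.14
- 1 v 49: 2.011 × √(1 + 1/49) = 2.03

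Adding treated subjects barely helps, because the 1/n1 = 1 term dominates.

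**Step 5: the control rate.** The exact (Clopper-Pearson) 95% CI is 0 to 97.5% if the one subject fails and 2.5 to 100% if that subject succeeds.

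The larger treated counts are best cases. The 20s are targets, and Section 6.1.2 allows a second eye to be re-enrolled in Group 3 or 4, so eyes may not be independent.

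**The case against.** The strongest reply is that this is stale wording in a small, open-label Phase 2 study. Section 9.1 disclaims statistical sizing, puts 16 v 8 in the past tense and aims only at preliminary estimates. Table 7 discloses the closure. Section 9.3 applies tests only where possible and defers the method to an SAP whose text is not available here, so a replacement contrast may exist there. Section 9.2 names no test or alpha, so the power figures rest on outside assumptions. A p-value below 0.05 is also not arithmetically impossible at 1 v 20 or 1 v 49.

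Part of this stands. The rates, test and alpha are assumed, and 49 is a ceiling. The SAP may name another contrast. The enrolled control's own reason for being in Group 1 is not given; only the assignment rule is. A Group 1 subject who rolled over to Group 1a would receive drug and so enter the Full Analysis Set, and Per Protocol membership could be read either way, so that point is one of unclear wording.

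The rest does not rescue the text. The limit on testing does not withdraw a promised comparison, and a difference against one person is uninterpretable with or without a p-value. A future SAP would inherit the commitment unless the protocol changes. The corner cases that reach significance need near-perfect treated response and would still rest on one non-randomised subject.

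**Conclusion.** The concern holds. Sections 9.2 and 9.3.1 commit to efficacy and safety comparisons that Table 7 has made unworkable, and no visible text withdraws or replaces them. The lack of a control variance and the non-randomised assignment follow from the documents alone. The power figures are conditional on the stated assumptions, but the conclusion is not sensitive to them: across the three rate pairs, power with one control runs from 0 to 11%, against 38 to 99% as planned, and the interval for a mean difference is more than twice as wide. Because this affects the only stated efficacy and safety contrast, it must be fixed before the SAP is finalised.

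**What to change.** 1. **Section 9.1.** Label 16 v 8 as the original plan, give the Table 7 numbers (1, 9, 20 and 20) and state the precision they offer. Illustrative exact 95% CIs, using hypothetical counts: 14/20 = 70% (46 to 88%); 11/16 = 69% (41 to 89%) if some eyes drop out for a descemetorhexis over 5 mm or for missing data; 6/9 = 67% (30 to 93%) for Group 2. Say that these treat eyes as independent.
2. **Sections 9.2 and 9.3.1.** Remove the efficacy and safety comparisons with control. List the single Group 1 subject descriptively. State that the trial cannot estimate TTHX1114 against DWEK/DSO alone. Bring the synopsis and the Group 1 text into line.
3. **Planned analysis.** Make per-group estimates with exact 95% CIs the planned analysis, which fits the by-group endpoint in Section 4.1 and the descriptive statistics in Section 9.2. Carry the same statement into the SAP.

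Optional, and not part of the required change: a Group 4 v Group 3 contrast or covariate adjustment, labelled exploratory and non-randomised, with calendar-time confounding and two-eye dependence noted.

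The cost is rewording of these sections and a matching SAP statement, with no new data or patients. The sponsor gives up a control comparison that it cannot support.
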